5.4 Removal of Subjects from Therapy or Assessment

5.4.1 Discontinuation of Individual Subjects

Each subject has the right to withdraw from the study at any time. In addition, the investigator may discontinue a subject from the study at any time if the investigator considers it necessary for any reason, including the occurrence of an adverse event or noncompliance with the protocol.

If, during the course of study drug administration, the subject prematurely discontinues (D/C), the procedures outlined for the applicable Premature D/C Visit should be completed as defined in [Appendix C](#). Ideally this should occur on the day of study drug discontinuation, but no later than 2 days after their final dose of study drug and prior to the initiation of any other anti-HCV therapy. However, these procedures should not interfere with the initiation of any new treatments or therapeutic modalities that the investigator feels are necessary to treat the subject's condition. Following discontinuation of study drug, the subject will be treated in accordance with the investigator's best clinical judgment. The last dose of any study drug and reason for discontinuation will be recorded in the EDC (electronic data capture) system. The subject should then begin the Post-Treatment Period where the subject will be monitored for 24 weeks for HCV RNA, the emergence and persistence of resistant viral variants.

If a subject is discontinued from study drugs or during the Post-Treatment Period with an ongoing adverse event or an unresolved laboratory result that is significantly outside of the reference range, the investigator will attempt to provide follow-up until a satisfactory clinical resolution of the laboratory result or adverse event is achieved.

In the event that a positive result is obtained on a pregnancy test for a subject or a subject reports becoming pregnant during the Treatment Period, the administration of RBV (if applicable) to that subject must be discontinued immediately. DAAs may be continued at the Principal Investigator's discretion after discussion with the subject, if the benefit of continuing DAAs is considered to outweigh the risk. Specific instructions regarding subject pregnancy can be found in [Section 6.1.6](#). Subjects will be monitored for SVR in

the Post-Treatment Period as described in Section 5.1.3. The investigator is also encouraged to report the pregnancy information to the voluntary RBV Pregnancy Registry.

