6.3 Missing Data Imputation

Missing Data Imputation for SVR

HCV RNA values will be selected for analysis based on the analysis windows defined in Section 6.2.

For analyses of SVR, subjects' missing visit values will have backward imputation applied, if possible. For backward imputation, if the nearest HCV RNA value after the SVR window is unquantifiable or undetectable, then it will be used to impute the HCV RNA value in the SVR window. If a subject is missing an HCV RNA value within the appropriate SVR window after performing backward imputation, then this value will be imputed with an HCV RNA value from a local laboratory if present; otherwise, the HCV RNA value will be missing. Subjects with missing HCV RNA data in the analysis window, after imputations, will be imputed as a failure.

Regardless of the imputation method described above, if a subject starts another treatment for HCV, then all HCV RNA values for this subject measured on or after the start date of the new HCV treatment will be excluded from analyses. The subject will be considered a failure for summaries of viral response at all time points after the start of the new HCV treatment.

Missing Data Imputation for Virologic Failure

If HCV RNA values from the central laboratory are missing but a local laboratory value is present in the appropriate time period, then the local laboratory value will be used to assess post-treatment relapse and on-treatment virologic failure.

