10.8 Resistance Analyses

10.8.1 HCV Drug-Resistance Analyses

For all subjects, full length NS3/4A and NS5A will be sequenced from baseline samples by next generation sequencing (NGS). For all subjects who experience virologic failure (on-treatment virologic failure or Relapse_{overall} as defined in Section 10.1), full length NS3/4A, NS5A and NS5B genes from the first sample after virologic failure with HCV RNA \geq 1000 IU/mL will be sequenced by NGS. For all other subjects who do not achieve SVR₁₂ or SVR₂₄ (for non-virologic failure reasons as defined in Section 10.1) but have a post-treatment time point with HCV RNA \geq 1000 IU/mL, full length NS3/4A, NS5A and NS5B genes from the first post-treatment sample with HCV RNA \geq 1000 IU/mL will also be sequenced by NGS.

For all subjects who do not achieve SVR₁₂ or SVR₂₄, a listing by subject that includes HCV genotype/subtype, reason for SVR₁₂ or SVR₂₄ non-response, baseline resistance data availability, and key baseline characteristics will be produced by treatment arm.

For each DAA target, signature amino acid positions and the key subset of amino acid positions for the respective inhibitor class are shown in Table 10. Appropriate subtype-specific prototypic reference sequences will be used for comparison with sequences from samples.

Table 10. Signature Amino Acid Positions and the Key Subsets of Amino Acid Positions

Target	Signature Amino Acid Positions	Key Subset of Amino Acid Positions
GT1 NS3	36, 43 (GT1a only), 54, 55, 56, 80, 107, 122, 132 (GT1a only), 155, 156, 158, 168, 170, 175 (GT1b only)	155, 156, 168 (all GTs)
GT2, 3, 4, 5, 6 NS3	36, 43, 54, 55, 56, 80, 155, 156, 166 (GT3 only), 168	
GT1 NS5A	24, 28, 29, 30, 31, 32, 54 (GT1b only), 58, 62, 92, 93	24, 28, 30, 31, 58, 92, 93 (all GTs)
GT2, 3, 4, 5, 6 NS5A	24, 28, 29, 30, 31, 32, 58, 92, 93	
GT1, 2, 3, 4, 5, 6 NS5B	96, 142, 159, 237, 282, 289, 320, 321	282

Included time points for analyses of samples from subjects who do not achieve SVR₁₂ are 1) the sample closest in time after failure/discontinuation with an HCV RNA level of ≥ 1000 IU/mL, and 2) 24 weeks post-DAA treatment, provided that resistance-associated substitutions were detected at the time of failure/discontinuation.

The following definitions will be used in the resistance analyses:

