- Baseline polymorphism: a polymorphism by NGS in a baseline sample ($\geq 2\%$ or $\geq 15\%$ prevalence within a subject's viral population depending on polymorphism frequency threshold utilized) that was not present in the appropriate prototypic reference amino acid sequence for a given DAA target (NS3, NS5A, or NS5B).
- Post-baseline substitution: an amino acid substitution in a post-baseline time point sample that was not detected at baseline ($< 2\%$) in the subject and is detectable in $\geq 2\%$ of the sequences from the post-baseline sample.

- Enriched variant: a variant present in both the baseline and a post-baseline sample whose prevalence in the post-baseline sample is at least 20 percentage points greater than the prevalence in the baseline sample [(post-baseline % – baseline %) \geq 20]
- Treatment-emergent substitution: A post-baseline substitution or an enriched variant.
- Substitution at signature amino acid position: a substitution in a post-baseline sample observed at \geq 2% prevalence within a subject's viral population that was not present in the appropriate prototypic reference amino acid sequence for a given DAA target (NS3/4A, NS5A, or NS5B).

Analysis 1

The following analyses will be performed for all subjects, separated by arm, HCV genotype/subtype, and previous treatment experience prior to enrolling in the AbbVie HCV parent study (including total):

- A listing of baseline polymorphisms (2% detection threshold) at signature amino acid positions for each DAA target (NS3, NS5A, and NS5B) in the ITT population. HCV genotype/subtype and treatment outcome (SVR₁₂ or reason for SVR₁₂ non-response) will also be displayed for each subject.
- The number and percentage of subjects with baseline polymorphisms at signature amino acid positions at detection thresholds of 2% and 15% for subjects in the ITT population. This analysis includes prevalence of each baseline polymorphism, and a summary of the number of subjects with polymorphisms in NS3 only, NS5A only, NS5B only, any in NS3, any in NS5A, any in NS5B, any in NS3 or NS5A or NS5B, any in NS3 + NS5A, any in NS3 + NS5B, any in NS5A + NS5B, and any in NS3 + NS5A + NS5B.

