- Total number and percentage of subjects in the ITT population with baseline polymorphisms *in the key subset of amino acid positions* at detection thresholds of 15% for subjects in the ITT population. This analysis summarizes the number of subjects with polymorphisms in NS3 only, NS5A only, NS5B only, any in NS3, any in NS5A, any in NS5B, any in NS3 or

NS5A or NS5B, any in NS3 + NS5A, any in NS3 + NS5B, any in NS5A + NS5B, and any in NS3 + NS5A + NS5B.

Analysis 2

The impact of baseline polymorphisms at the *key subset of amino acid positions* on treatment outcome (the SVR₁₂ rate) will be assessed for the **mITT-VF** population by presenting the SVR₁₂ rates for the following groups, using detection thresholds of 2% and 15%, separated by arm, HCV genotype/subtype (including total), and previous treatment experience prior to enrolling in the AbbVie HCV parent study:

- in NS3 only versus none in NS3, NS5A, or NS5B
- in NS5A only versus none in NS3, NS5A, or NS5B
- in NS5B only compared to none in NS3, NS5A, or NS5B
- any in both NS3 and NS5A versus none in NS3 or NS5A
- any in both NS3 and NS5B versus none in NS3 or NS5B
- any in both NS5A and NS5B versus none in NS5A or NS5B
- any in each of NS3, NS5A and NS5B versus none in NS3, NS5A, or NS5B
- any in NS3 versus none in NS3
- any in NS5A versus none in NS5A
- any in NS5B versus none in NS5B
- any in NS3 or NS5A or NS5B versus none in NS3, NS5A, or NS5B

Analysis 3

The following listings will be produced for subjects who do not achieve SVR₁₂ or SVR₂₄ and have post-baseline resistance data available. HCV genotype/subtype and reason for SVR₁₂ or SVR₂₄ non-response will be displayed for each subject by treatment, and previous treatment experience prior to enrolling in the AbbVie HCV parent study.

- Listing by subject and time point of all *treatment-emergent substitutions* relative to the baseline amino acid sequence will be provided for each DAA target (NS3, NS5A, and NS5B).
- Listing by subject and time point of all *substitutions at signature amino acid positions* in a post-baseline time point relative to the appropriate prototypic reference amino acid sequence will be provided for each DAA target (NS3, NS5A, and NS5B).

HCV Genotype/Subtype

Phylogenetic analysis will be conducted on HCV sequences from baseline samples for all subjects in order to accurately determine subtype.

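### The resistance analyses in SAP 10.8.1 have no cutoff at the start of a new HCV treatment, so substitutions selected by a later regimen could be listed as emergent, or read as persistent, after the study regimen

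*SAP*

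**What the plan says.** **Which samples are sequenced.** For subjects who do not achieve SVR12, SAP 10.8.1 uses "the sample closest in time after failure/discontinuation with an HCV RNA level of ≥ 1000 IU/mL" and then a sample "24 weeks post-DAA treatment, provided that resistance-associated substitutions were detected at the time of failure/discontinuation". Neither carries a condition about new HCV treatment. Table 5 of SAP 6.2 gives the Post-Treatment Week 24 resistance window as Study Drug End Day 127 to 999. Protocol 8.1.3 limits sequencing to samples with HCV RNA of at least 1000 IU/mL and assesses persistence of variants at Post-Treatment Week 24.

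**How findings are labelled.** SAP 10.8.1 defines a post-baseline substitution as "an amino acid substitution in a post-baseline time point sample that was not detected at baseline", and then: "Treatment-emergent substitution: A post-baseline substitution or an enriched variant". Analysis 3 lists these by subject and time point.

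**What happens at new HCV treatment.** The only rule is in SAP 6.3, under the heading on imputation for SVR: "all HCV RNA values for this subject measured on or after the start date of the new HCV treatment will be excluded from analyses". Its stated consequence is "The subject will be considered a failure for summaries of viral response at all time points after the start of the new HCV treatment".

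**Whether new treatment can start during follow-up.** Protocol 5.2.3.4 bars other anti-HCV drugs only during the Treatment Period. Protocol 5.2.3 has HCV antivirals recorded beyond 30 days after treatment, and SAP 7.3 defines an eCRF entry for post-treatment HCV medication.

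**The concern.** The SAP accepts that a virologic measurement made after a new HCV treatment no longer describes the study regimen, and it removes HCV RNA on that ground. A viral sequence from the same blood draw has the same problem, yet 10.8.1 keeps it and gives it a label that attributes it to the study drugs.

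Emergence and persistence of resistant variants are among the stated purposes of the 24-week follow-up (Protocol 5.1 and 5.1.3), alongside safety and HCV RNA. The data will come from very few subjects, so one misattributed sequence could shape what is concluded about resistance after this regimen. The items that SAP 10.8.1 specifies for the Analysis 3 listings are genotype and subtype, reason for non-response, treatment, and experience before the parent study. New HCV treatment is not among them, so the listing alone would not reveal the problem.

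**Working it through.** The point rests on text, so the relevant rules are set side by side.

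| Question | HCV RNA (SAP 6.3) | Sequences (SAP 10.8.1) |
|---|---|---|
| Cutoff at new HCV treatment? | Yes, on or after its start date | None stated |
| Effect on the subject | Counted as failure afterwards | Remains eligible for sequencing as a non-responder |
| Latest day for the 24-week time point (Table 5) | Day 210 for SVR24 | Day 999 |

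**Worked case.** A subject relapses at Post-Treatment Week 4, starts another regimen before Post-Treatment Week 24, and has HCV RNA of at least 1000 IU/mL at the Week 24 visit.

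1. Under 6.3, the Week 24 HCV RNA value is dropped and the subject is a failure for SVR24.
2. Under 10.8.1, the Week 24 sample is sequenced if substitutions were detected at failure.
3. A substition absent at baseline and at failure but present at Week 24 meets the treatment-emergent definition, even if the new regimen selected it.
4. A substitution present at failure and maintained by the new regimen would look persistent under Protocol 8.1.3.

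**Conditions for the Week 24 sample.** All four must hold: non-response; substitutions detected at failure or discontinuation; new treatment started before the sample; and HCV RNA still at least 1000 IU/mL. A subject suppressed on the new regimen is not sequenced.

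**The first sample.** It is exposed only if no sample between failure and the start of new treatment reached 1000 IU/mL. That is possible but should be less common.

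**Window length.** Resistance at Week 24: 999 − 127 + 1 = 873 days. SVR24: 210 − 127 + 1 = 84 days. Table 5 takes the resistance result closest to Day 168, so the long tail matters only for subjects without a nearer sample.

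**Scale.** SAP 4.3 expects fewer than 5 SVR12 non-responders. One affected subject would be 1/4 = 25%, 1/3 = 33.3%, 1/2 = 50% or 1/1 = 100% of 4, 3, 2 or 1 non-responders. These are shares of subjects. They are not shares of the at-failure sequences.

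**The case against.** **SAP 6.3 may already cover this.** Its exclusion is worded as applying to analyses generally, sample selection depends on an HCV RNA level, and Table 5 windows HCV RNA and resistance together. On that reading a post-treatment-switch value could not qualify a sample. The reading is arguable, but the text does not say it. The rule sits under SVR imputation, its stated consequence concerns viral response, and the SAP's 24-week time point states no HCV RNA threshold of its own. If two programmers could read it differently, the sentence is still needed.

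**A sample before new treatment is planned.** Protocol 5.4.1 puts the premature discontinuation visit no later than 2 days after the final dose and before other anti-HCV therapy, and Appendix C collects a resistance sample there. The clause "these procedures should not interfere with the initiation of any new treatments or therapeutic modalities" is an exception to that rule and concerns subjects who stop study drug early; it does not itself address relapse after completed treatment. This stands: it protects much of the at-failure data for on-treatment failures. It does not protect the Week 24 sample.

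**The outputs are listings by time point.** At-failure and Week 24 rows stay separate, and the SAP plans no persistence rate. This also stands and limits the harm. A reader could see that a substitution appeared only at Week 24, but would not see from the specified items that another regimen had intervened.

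**A stronger reading to avoid.** A reader might infer that later-selected substitutions will be listed, or that one retreated subject would make up 25% to 100% of the resistance-at-failure data. The documents do not support either. The effect needs several conditions together, no retreatment rate is given, and the at-failure sample will often come before any new treatment.

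**Conclusion.** The gap is real but conditional. Followed literally, SAP 10.8.1 could label substitutions selected by a later HCV regimen as emergent on the study regimen, or allow them to be read as persistent after it. The exposure lies mainly in the Post-Treatment Week 24 sample, and less often in a delayed first sample of at least 1000 IU/mL.

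The number of subjects affected cannot be derived. An assumed range of 0 to 4 follows from the expectation of fewer than 5 SVR12 non-responders. That count includes non-virologic reasons for non-response, and Analysis 3 also takes in SVR24 non-responders, so the range is a guide and not a bound.

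SVR12, on-treatment virologic failure and relapse are unaffected by this gap. The change is worth making because the resistance data are scarce and the SAP already accepts the principle in 6.3.

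**What to change.** Add to SAP 10.8.1 that samples collected on or after the start date of any new HCV treatment, the same cutoff as in 6.3, are not counted as treatment-emergent and are not used to assess persistence. Where such samples have been sequenced, show them flagged in the Analysis 3 listings or in a separate listing, with the new regimen named. Apply the rule to both the first post-failure sample and the Week 24 sample.

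The cost is one sentence and one date comparison in programming, using medication records already collected under Protocol 5.2.3 and SAP 7.3. Some Week 24 sequences may leave the persistence assessment, but they remain visible in the flagged or separate listing.

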For all subjects, the following will be provided:

- The number and percentage of subjects with baseline variants at detection-thresholds of $\geq 2\%$ and $\geq 15\%$ for variants at signature amino acid positions, and $\geq 15\%$ for variants at non-signature positions.
- A listing of all baseline variants ($\geq 2\%$ detection threshold) at signature resistance-associated amino acid positions for each DAA target.

- A listing of all baseline variants ($\geq 15\%$ detection threshold) at non-signature resistance-associated amino acid positions for each DAA target.
- A listing of subjects with multiple baseline variants at signature amino acid positions (each at $\geq 15\%$ prevalence within a subject's viral population), either within a DAA target or across any 3 DAA targets.
- The impact of baseline variants on treatment outcome will be assessed as follows: for each variant, the SVR₁₂ rate will be calculated for subjects with and without the variant and the 2 rates will be compared. Analyses will be grouped by subject's HCV subtype and DAA target. Subjects not achieving SVR₁₂ due to non-virologic reasons will be excluded from this analysis. These analyses will be performed based on the following criteria:
 - An analysis will be performed based on amino acid position, using detection thresholds of $\geq 2\%$ and $\geq 15\%$ for all variants at each signature amino acid position and a detection threshold of $\geq 15\%$ for all variants at each non-signature amino acid position.
 - An additional analysis will be performed using detection thresholds of $\geq 2\%$ and $\geq 15\%$ for the impact of each specific variant as specified by clinical virology.

The following will be provided for subjects who do not achieve SVR₁₂ and have post-baseline resistance data available:

- A listing by subject of all treatment-emergent variants relative to the baseline sequence will be provided for each DAA target
- A listing by subject of all variants at signature amino acid positions
- The number and percentage of subjects (with subject listing) with variants emerging at an amino acid position relative to baseline
- The number and percentage of subjects (with subject listing) with certain specific emerged variants

The persistence of post-baseline variants at signature resistance-associated amino acid positions for each target will be assessed by NGS at Post-Treatment Week 24. A listing

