SVR₄ = HCV RNA < LLOQ in the SVR₄ window (4 weeks after the last actual dose of study drug) without any confirmed quantifiable (\geq LLOQ) post-treatment value before or during that SVR window.

SVR₁₂ = HCV RNA < LLOQ in the SVR₁₂ window (12 weeks after the last actual dose of study drug) without any confirmed quantifiable (\geq LLOQ) post-treatment value before or during that SVR window.

SVR₂₄ = HCV RNA < LLOQ in the SVR₂₄ window (24 weeks after the last actual dose of study drug) without any confirmed quantifiable (\geq LLOQ) post-treatment value before or during that SVR window.

Relapse₁₂ = confirmed HCV RNA \geq LLOQ between end of treatment and 12 weeks after last actual dose of study drug (up to and including the SVR₁₂ window) for a subject with HCV RNA < LLOQ at Final Treatment Visit who completed treatment, excluding reinfection as described below.

Relapse₂₄ = confirmed HCV RNA \geq LLOQ within the SVR₂₄ window for a subject who achieved SVR₁₂ and has HCV RNA data available in the SVR₂₄ window, excluding reinfection.

Relapse_{overall} = confirmed HCV RNA \geq LLOQ between end of treatment and up to and including the last HCV RNA measurement collected in the Post-Treatment Period for a subject with HCV RNA < LLOQ at Final Treatment Visit who completed treatment, excluding reinfection.

Virologic failure = On-treatment virologic failure or Relapse_{overall}

Only subjects who have at least one post-treatment HCV RNA value will be included in analyses of relapse. For the analysis of relapse, completion of treatment is defined as any subject with study drug duration of 77 days or greater for Arm A and 103 days or greater for Arm B. If the last available post-treatment value is \geq LLOQ, then the subject will be considered a relapse (i.e., will not require confirmation).

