HCV reinfection is defined as confirmed HCV RNA \geq LLOQ after the end of treatment in a subject who had HCV RNA $<$ LLOQ at Final Treatment Visit, along with the post-treatment detection of a different HCV genotype, subtype, or clade compared with baseline, as determined by phylogenetic analysis of the NS3/4A, and/or NS5A, and/or NS5B gene sequences. Reinfection in the case of the same HCV subtype is defined as a clade switch, as indicated by the lack of clustering between the baseline and post-treatment sequences by phylogenetic analysis. If phylogenetic analysis is not possible due to technical difficulties, HCV reinfection may be determined with a confirmed HCV genotype or subgenotype switch by the Versant HCV Genotype Inno-LiPA Assay v2.0 or Sanger assay.

Post-treatment relapse is defined as described earlier (**Relapse₁₂**, **Relapse₂₄**, **Relapse_{overall}**), and no genotype, subtype, or clade switch compared with baseline as determined by phylogenetic analysis of the NS3/4A, and/or NS5A, and/or NS5B gene sequences. If phylogenetic analysis is not possible due to technical difficulties, the subject will be defined as having a post-treatment relapse unless an HCV genotype or subgenotype switch is confirmed by the Versant HCV Genotype Inno-LiPA Assay v2.0 or Sanger assay.

Reasons for SVR₁₂ Non-Response

Subjects who do not achieve SVR₁₂ (SVR₁₂ non-responders) will be categorized as having:

1. On-treatment virologic failure;
2. HCV reinfection;

3. Relapse₁₂;
4. Prematurely discontinued study drug with no on-treatment virologic failure (defined as any SVR₁₂ non-responder who prematurely discontinued study drug [study drug duration < 77 days for Arm A, or < 103 days for Arm B] and did not meet the **On-treatment virologic failure or HCV reinfection** definitions);
5. Missing follow-up data in the SVR₁₂ window (defined as any subject who completed study drug without data in the SVR₁₂ window after applying the imputation rules and not meeting the definitions of [1], [2], [3], or [4]);
6. Other (defined as any SVR₁₂ non-responder not meeting the definitions of [1] – [5]).

Reasons for SVR₂₄ Non-Response

Subjects who do not achieve SVR₂₄ (SVR₂₄ non-responders) will be categorized as having:

1. On-treatment virologic failure;
2. HCV reinfection;
3. Relapse₁₂;
4. Relapse₂₄;

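### SAP 10.8.1 Analysis 3 would label the strain differences of an HCV-reinfected subject as treatment-emergent substitutions, because reinfection is not excluded from that listing

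*SAP*

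**What the plan says.** **Who is a non-responder.** SAP 10.1 introduces the reasons for non-response with "Subjects who do not achieve SVR₁₂ (SVR₁₂ non-responders) will be categorized as having" and places HCV reinfection second, after on-treatment virologic failure and ahead of Relapse12. The SVR24 list has it in the same place. Reinfection requires confirmed quantifiable HCV RNA after treatment together with "detection of a different HCV genotype, subtype, or clade compared with baseline". All relapse definitions exclude it, and since virologic failure means on-treatment failure or overall relapse, it falls outside virologic failure as well.

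**Who is sequenced.** SAP 10.8.1 sequences NS3/4A, NS5A and NS5B after virologic failure. It then extends this to a second group: "For all other subjects who do not achieve SVR₁₂ or SVR₂₄ (for non-virologic failure reasons as defined in Section 10.1", provided a post-treatment sample reaches 1000 IU/mL.

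**What counts as emergent.** SAP 10.8.1: "Treatment-emergent substitution: A post-baseline substitution or an enriched variant". A post-baseline substitution is one below 2% at baseline and at 2% or more later. An enriched variant has risen by at least 20 percentage points. Protocol 8.1.3 uses the same rule.

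**What is reported.** Analysis 3 opens with "The following listings will be produced for subjects who do not achieve SVR₁₂ or SVR₂₄ and have post-baseline resistance data available" and specifies two by-subject listings: treatment-emergent substitutions relative to baseline, and substitutions at signature positions relative to a reference sequence. Genotype/subtype and reason for non-response appear beside each subject. Protocol 8.1.3, for SVR12 non-responders with post-baseline resistance data, also asks for a count: "The number and percentage of subjects (with subject listing) with variants emerging at an amino acid position relative to baseline".

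**The concern.** The emergence rule has two inputs, the baseline sequence and a later sequence from the same subject. It assumes that the later virus descends from the earlier one. For a relapse or a breakthrough that is reasonable. For a reinfection it is false by the plan's own definition, so the rule would fire because the strain is new, whether or not study drug selected anything.

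Following the emergence and persistence of resistance is a stated purpose of the 24-week post-treatment period (protocol 5.1 and 5.1.3), and SAP 4.3 expects fewer than 5 SVR12 non-responders among about 50 subjects. In so small a resistance set, one mislabelled subject could supply a large share of the substitutions reported as emerging after this regimen.

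**Working it through.** **Step 1: trace one reinfected subject with HCV RNA of at least 1000 IU/mL through the plan.**

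1. The subject is an SVR12 or SVR24 non-responder, reason 2 (SAP 10.1).
2. The subject is not a virologic failure, so enters sequencing through the second group (SAP 10.8.1).
3. Any residue of the new strain that was below 2% at baseline and is now at 2% or more is a post-baseline substitution, hence treatment-emergent (SAP 10.8.1 definitions).
4. The subject meets the Analysis 3 population and is listed.
5. If the subject is an SVR12 non-responder, the population stated for the protocol 8.1.3 counts also includes the subject. A reinfection first seen after the SVR12 window reaches only the SAP listing, through SVR24 non-response.

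**Step 2: look for an exclusion elsewhere.** Two sentences come close, and neither applies:

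- Protocol 8.1.2.2 has reinfections summarized separately, but under the relapse endpoint.
- Protocol 8.1.3 drops subjects who missed SVR12 for non-virologic reasons, but only from the analysis of baseline variants against outcome. SAP Analysis 2 does the equivalent by using mITT-VF.

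Nothing excludes reinfection from the emergent-substitution outputs.

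**Step 3: how often would the rule fire at signature positions?** The plan gives no figure to reproduce. The positions come from SAP Table 10 for GT1a:

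- NS3: 36, 43, 54, 55, 56, 80, 107, 122, 132, 155, 156, 158, 168, 170 = 14
- NS5A: 24, 28, 29, 30, 31, 32, 58, 62, 92, 93 = 10
- Total L = 24

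The 8 NS5B positions are left out because the baseline sequencing commitment in SAP 10.8.1 names only NS3/4A and NS5A.

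Let d be the fraction of positions at which the new strain carries a residue not detected at baseline. This is an assumption, shown over a range and treated as uniform and independent across positions. P(at least one false emergent substitution) = 1 − (1 − d)^24.

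| d | Calculation | Chance |
|---|---|---|
| 1% | 1 − 0.99^24 | 21% |
| 2% | 1 − 0.98^24 | 38% |
| 5% | 1 − 0.95^24 | 71% |
| 10% | 1 − 0.90^24 | 92% |

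The first listing is not confined to signature positions, so the chance of any false entry in it is higher than this.

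**Step 4: effect on a protocol 8.1.3 percentage, if produced.** Assume k sequenced SVR12 non-responders, one of them reinfected with a strain that differs at the position in question, and no true emergent variant there in the others. The percentage is 1/k with the reinfected subject and 0/(k − 1) without.

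| k | Reinfected subject included | Excluded |
|---|---|---|
| 2 | 1/2 = 50% | 0/1 = 0% |
| 3 | 1/3 = 33% | 0/2 = 0% |
| 4 | 1/4 = 25% | 0/3 = 0% |

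k stops at 4 because SAP 4.3 expects fewer than 5 non-responders.

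**The case against.** The strongest reply is that the listing already discloses the problem. Each row carries the genotype/subtype and the reason for non-response, a second listing of all non-responders repeats the reason, and with so few subjects each row will be read individually. The definition of treatment-emergent is a comparison with baseline and makes no causal claim. The second Analysis 3 listing already compares with a reference sequence, so part of the remedy exists. Where the SAP relates resistance to outcome, it uses mITT-VF, which leaves reinfection out.

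Most of this stands as a limit on impact. It does not remove the defect: the output would still label as treatment-emergent differences that cannot show what the drug selected, and the reader would have to undo the label. Nor does the SAP say whether the reference and the genotype-specific positions in Table 10 should follow the old strain or the new one.

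A reader might infer that an emergent-variant percentage in the planned analysis is distorted. The SAP does not plan one. Analysis 3 contains listings only, the count stands in protocol 8.1.3 alone, and SAP 12.1 item 4 says that the resistance analyses were updated. Inclusion in the protocol count is also not fully determined, because its time points are anchored to failure or discontinuation and a reinfected subject who completed treatment may have neither.

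A reader might also infer that a reinfection is likely, or that a false entry at a signature position is nearly certain. The documents give neither a reinfection rate nor a strain divergence, so neither inference is supported.

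**Conclusion.** The concern holds as a labelling and population error in the resistance outputs. As written, a reinfected subject with a sequenced post-treatment sample goes into the treatment-emergent listing with no exclusion. The same subject would fall in the population stated for the protocol counts if those are produced.

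The consequence is contingent and bounded. It requires a reinfection at 1000 IU/mL or more within follow-up. The chances in Step 3 rest on assumed divergence and on independence across positions, and the shifts in Step 4 on the assumed mix of non-responders. The trace in Step 1 needs none of these.

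It should not be read as a threat to the efficacy conclusions or as a contradiction of them. SVR12, on-treatment failure and relapse do not use the emergence rule, and Analysis 2 already excludes reinfection through mITT-VF. The correction is still worth making before database lock, because it costs almost nothing and the resistance set is expected to be very small.

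**What to change.** - In SAP 10.8.1 Analysis 3, exclude subjects classified as HCV reinfection from the treatment-emergent and enriched outputs.
- If the protocol 8.1.3 emergent-variant counts and persistence outputs are produced, apply the same exclusion to numerator and denominator.
- Keep sequencing these subjects, since the phylogenetic classification depends on it.
- List their post-treatment sequences separately, against the reference for the reinfecting subtype, under a title that identifies them as the reinfecting strain.

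The cost is one sentence in the SAP, one population flag in programming and one short extra listing if a reinfection occurs. No additional samples, visits or subjects are needed.
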